3.3.2 Patient Withdrawal

All patients are free to withdraw from participation in the study at any time, for any reason, specified or unspecified, and without prejudice to further treatment. The Investigator may end this study at any time, for any reason.

4. STUDY TREATMENTS

4.1 Treatments Administered

Patients will receive Dabrafenib (150 mg PO BID), Trametinib (2 mg PO QD) and Metformin (500 mg PO BID x 2 weeks, then 850 mg PO BID). Treatment will continue until progression, unless the patient experiences unacceptable toxicity. Patients will be evaluated for (1) clinical response, (2) safety, and (3) survival.

4.2 Description of Dabrafenib

Dabrafenib is an inhibitor of some mutated forms of BRAF kinases with in vitro IC50 values of 0.65, 0.5, and 1.84 nM for BRAF V600E, BRAF V600K, and BRAF V600D enzymes, respectively. Dabrafenib also inhibits wild-type BRAF and CRAF kinases with IC50 values of 3.2 and 5.0 nM, respectively, and other kinases such as SIK1, NEK11, and LIMK1 at higher concentrations. Some mutations in the BRAF gene, including those that result in BRAF V600E, can result in constitutively activated BRAF kinases that may stimulate tumor cell growth. Dabrafenib inhibits BRAF V600 mutation-positive melanoma cell growth in vitro and in vivo.

4.3 Side Effects, Warnings and Precautions of Dabrafenib.

As stated in the manufacturer's package insert for the FDA-approved Dabrafenib:

New Primary Cutaneous Malignancies: Across clinical trials of Dabrafenib (n = 586), the incidence of cutaneous Squamous Cell Carcinoma was 11%.

Serious Febrile Drug Reactions: The incidence of fever (serious and non-serious) was 28% in patients treated with dabrafenib. Withhold Trametinib for fever of 101.3°F or greater or for any serious febrile drug reaction and evaluate for signs and symptoms of infection.

Hyperglycemia: The incidence of Grade 3 hyperglycemia based on laboratory values was 6% (12/187) in patients treated with dabrafenib.

Ophthalmologic Reactions: Uveitis and Iritis occurred in 1% (6/586) of patients treated with dabrafenib across clinical trials.

Hemolytic Anemia: Dabrafenib, which contains a sulfonamide moiety, confers a potential risk of hemolytic anemia in patients with glucose-6-phosphate dehydrogenase (G6PD) deficiency.

4.4 Description of Trametinib

Reversibly and selectively inhibits mitogen-activated extracellular kinase (MEK) 1 and 2 activation and kinase activity. MEK is a downstream effector of the protein kinase B-raf (BRAF); BRAF V600 mutations result in constitutive activation of the BRAF pathway (including MEK1 and MEK2). Through inhibition of MEK 1 and 2 kinase activity, trametinib causes decreased cellular proliferation, cell cycle arrest, and increased apoptosis. The combination of trametinib and dabrafenib allows for greater inhibition of the MAPK pathway, resulting in BRAF V600 melanoma cell death.

4.5 Side Effects, Warnings and Precautions of Trametinib.

As stated in the manufacturer's insert for the FDA-approved Trametinib:

Cardiovascular: Hypertension (15%) and Cardiomyopathy

Dermatologic: Skin rash (57%)

Endocrine & metabolic: Hypoalbuminemia (42%)

Gastrointestinal: Diarrhea (43%)

Hematologic & oncologic: Anemia (38%)

Hepatic: Increased serum AST (60%)

4.6 Description of Metformin

A complex I inhibitor that decreases hepatic glucose production, decreasing intestinal absorption of glucose and improves insulin sensitivity (increases peripheral glucose uptake and utilization).

4.7 Side Effects, Warnings and Precautions of Metformin.

Gastrointestinal: Diarrhea (12% to 53%); nausea/vomiting (7% to 26%; 7% to 9%); flatulence (12%)

Neuromuscular & skeletal: Weakness (9%)

4.8 Dose Delays and Modifications

Dose delays and modifications of each of the three drugs in this combination regimen will be at the Investigator's discretion. Investigators will refer to the dosing guidelines in the package inserts for guidance on dosing decisions.

4.9 Concomitant Medications

Concomitant medications and treatment (for example, palliative radiotherapy) during the study will be allowed at the Principal Investigator's discretion.

5. EFFICACY AND SAFETY MEASURES

5.1 Schedule of Events

A schedule of events is presented in Appendix 1.

5.2 Efficacy Measures

This study includes assessments of safety and efficacy as outlined in the sections below. Disease progression and efficacy response will be determined using RECIST 1.1.

5.2.1 Primary Efficacy Endpoints

The primary efficacy endpoints are RECIST 1.1 and safety. Efficacy responses will be assessed following the last administration of the test agents.

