Diagnosis and entry criteria:	
Exclusion Criteria
 
Patients will not be entered in the study for any of the following:
 
 1. Prior treatment with Vemurafenib or Dabrafenib 2. Known hypersensitivity to Metformin or any of its components; 3. Received radiotherapy for non CNS disease within the 2 weeks prior to commencing study treatment or have not recovered from side effects of all radiation-related toxicities to Grade ≤ 1, except for alopecia; 4. Pregnant, breast-feeding, or refusing double barrier contraception, oral contraceptives, or avoidance of pregnancy measures; 5. Have any other uncontrolled infection or medical condition that could interfere with the conduct of the study.
Test product, dose and mode of administration:	Dabrafenib (150 mg PO BID) and Trametinib (2 mg PO QD) in combination with Metformin (500 mg PO BID x 2 weeks, then 850 mg PO BID) until progression.
Reference therapy:	Dabrafenib and Trametinib without Metformin.
Duration of treatment:	
 • Pre-treatment phase: An up to 42-day Screening period for collection of Baseline assessments (scans prior to study enrollment may be used for baseline measurement); • Treatment phase: Treatment period of 28-day cycles until progression unless unacceptable toxicity; • Follow-up phase: Patients will be followed for survival for a period of up to 3 years.
Criteria for evaluation:	
Efficacy Assessments
 
Tumor response and disease progression will be determined by the Investigator using objective radiologic criteria (Investigator assessed review of CT scans). Disease response or progression will be determined according to RECIST 1.1. An MRI will be used only if CT scans are not appropriate or CT scan results are not conclusive.
 
Primary efficacy endpoint: RECIST 1.1 objective response rates
 
Secondary efficacy endpoint: Overall survival
 
Pharmacokinetic Not applicable.
 
Pharmacodynamic

Criteria for evaluation (continued):	Not applicable Safety Safety will be assessed by the monitoring and recording of all adverse events (AEs) and serious adverse events (SAEs), regular monitoring of hematology, blood chemistry, regular measurement of vital signs, and the performance of physical examinations.

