3.1.1 Dose-Schedules

Patients will receive Dabrafenib (150 mg PO BID), Trametinib (2 mg PO QD) and Metformin (500 mg PO BID x 2 weeks, then 850 mg PO BID). Treatment will continue until progression, unless the patient experiences unacceptable toxicity. Patients will be evaluated for (1) clinical response, (2) safety, and (3) survival.

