6. STATISTICS

6.1 Study Design:

The study will be a single-arm, single center, uncontrolled phase I/II trial to estimate the safety of the combined treatments and then estimate the efficacy in terms of objective response (CR+PR) rate in patients with stage IIIC and Stage IV melanoma treated with dabrafenib/trametinib and metformin.

6.2 End-Point Definitions:

We will use two main end points. The primary endpoint of interest is the clinical response as defined in Section 5. The second end point will be tolerability to treatment. Secondary end points to be considered are the overall survival, OS, which is the time to first event or death due to any reason.

6.3 Sample Size:

The study is conducted in 2 phases.

Phase I:

In phase I, we will enroll 6 patients for the combination regimen of Dabrafenib/Trametinib/Metformin. We will allow at the most two drug-related CTCAE grade 4 toxicities in 6 patients in order to advance to Phase II. If we observe any drug-related deaths or more than two drug-related CTCAE grade 4 events, then we will halt the trial.

The Data and Safety Monitoring Plan of the Brown Cancer Center will be used for this phase I/II protocol. The investigators will conduct continuous review of data and patient safety at weekly meetings where the results of each patient's treatment are discussed. The discussion will include the number of patients, significant toxicities as described in the protocol, dose adjustments, and responses observed. Quarterly summaries of SAEs will be submitted through the CTO to the DSMC for review.

Phase II:

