Descriptive statistics related to the participant characteristics, treatment, and prognostic factors will be reported. Clinical response rates (complete, partial, and sustained) along with 95% confidence intervals will be estimated. The overall survival will be estimated by the Kaplan-Meier method²⁹. Differences in survival will be evaluated through the estimated hazard rates using the un-weighted log-rank tests. The OS time will be determined as the time from enrollment until death or last follow-up evaluation. In order to examine the significant prognostic factors, we will use the Cox proportional hazards regression models in both uni-variable and multi-variable setting³⁰. Descriptive statistics associated with the toxic events will be reported. The factors to be analyzed are ethnicity, gender, age, and pathological subtype. The various factors will be placed into categorical variables.

All calculations will be performed with SAS statistical software (SAS Institute Inc., Cary, NC). Analyses for specific aims are outlined below.

Statistical Analysis for specific aims:

Primary Objectives:

- *To evaluate the safety of the FDA-approved Dabrafenib and Trametinib in combination with Metformin in patients with unresectable Stage IIIC and Stage IV melanoma (Phase I).*

A total of 6 consecutive patients will be evaluated on this combination treatment. If any drug-related death occurs in this early stage, the study will be suspended. To continue on Phase II, at the most two drug-related CTCAE grade 4 events are allowed, which is in line with a Typical Phase I study with only one dose.

- *To estimate the efficacy of the Trametinib/Dabrafenib/Metformin regimen (Phase II).*

The efficacy will be estimated based on objective response (OR) rate, which is PR+ CR. We will estimate the OR rate along with its 95% confidence interval. We will also estimate CR and PR rates along with 95% confidence intervals. We will also compare these rates with published rates NEJM (2011)⁸ by comparing the confidence intervals.

- *To monitor the safety the combined regimens (Phase I/II).*

The monitoring rule is outlined in the next subsection.

Secondary Objective:

- *To estimate the overall survival rate on the combined regimes.*

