We will estimate the overall survival (OS) rates using the method of Kaplan-Meier. To compare the results with historical controls (results published in NEJM, 2011 and others), we need to estimate fixed term (such as 1-year, 2-year) OS rate along with 95% confidence interval precisely, that we plan to do using the method of Yuan and Rai (2011)³¹

- *To describe the toxicities.*

We will produce frequency and percentages of different CTCAE.

- *To explore the effect of other covariates (demographic, disease and treatment related) on objective response rate and toxicity and overall survival.*

We will identify the covariates and define specific groups, using some cut-offs, that are meaningful in a regression analysis. The effect of the covariates on a dichotomous outcome (OR or Toxicity) and time-to-event (OS) will be explored using a logistic regression and Cox proportional Hazards model, respectively.

6.6 Monitoring Rule for Phase II:

Safety monitoring of the accumulated outcomes data is designed to ensure the continuing safety of the currently enrolled participants and participants not yet enrolled. This is achieved by stopping the trial early to reduce the number of participants exposed to a harmful or ineffective treatment.

6.7 Non-efficacious Treatment (Futility):

In the combined regimen Dabrafenib/Trametinib/Metformin: in the first stage we will enroll 28 participants and if we observe at most 12 objective responses we will not enroll any new participants. If we observe 13 or more objective responses in the first stage, then we plan to enroll an additional 25 patients. In order for the treatment to be declared effective there has to be objective responses in at least 29 patients. If the objective response rate is only 41%, we will have 66% chance of stopping the study early and, at most, 37 patients will be treated on the potentially ineffective therapy.

6.8 Toxic Treatment (Safety) for Combined Phase I/II Trial:

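### Section 5.2.1 times the primary response after the last dose, and no passage states the best-response rule that the two-stage design appears to intend

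*Combined protocol and SAP*

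**What the plan says.** Section 5.2.1 consists of two sentences: "The primary efficacy endpoints are RECIST 1.1 and safety", then "Efficacy responses will be assessed following the last administration of the test agents". The second is the only statement in the protocol of when the primary response is assessed. On duration of treatment, Section 3.1.1 says "Treatment will continue until progression, unless the patient experiences unacceptable toxicity", and Section 4.1 repeats it.

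Other passages say which categories count, but not at which assessment:

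- The synopsis gives the primary efficacy endpoint as "RECIST 1.1 objective response rates".
- Section 6.2 sends the reader back: "The primary endpoint of interest is the clinical response as defined in Section 5".
- Section 6.5 says "The efficacy will be estimated based on objective response (OR) rate, which is PR+ CR".
- Section 5.2.3 schedules CT at entry, every 2 months on treatment, after the last administration and on clinical suspicion of progression. It defines CR, PR, SD and PD, but not which scan decides whether a patient is a responder.

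Two passages use responses while the trial is running. Under Section 6.3 the investigators' weekly meetings cover "dose adjustments, and responses observed". The two-stage rule (Table S1 and Section 6.7) acts on a count taken partway through, for example "If we observe 13 or more objective responses in the first stage".

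**The concern.** A set of response criteria is not an endpoint. An endpoint also needs the measure taken from the criteria and the period over which it is taken. Section 5.2.1 supplies only a time, and that time fits badly with treatment until progression. For a patient who stops because of progression, a scan after the last dose shows progression, whatever response came before. A responder still on treatment has had no last dose and so has no response to count.

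The design rests on a count of responders against fixed limits. P0 = 0.64, P1 = 0.80 and the published 76% are all given as objective response rates. If two people applying the protocol could count different patients as responders, the stage 1 decision and the final decision are not fully specified. Stage 1 is exposed first: at the planned 30 patients per year, 20 patients enrol in 20/30 × 12 = 8 months, when some responders may well still be on treatment.

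**Working it through.** **1. Reproduce Table S1.** Inputs (Section 6.3, Table S1): 20 patients at stage 1, drug rejected at 13 or fewer responses; 53 in total, rejected at 39 or fewer; P0 = 0.64, P1 = 0.80. With X1 ~ Bin(20, p) and X2 ~ Bin(33, p):

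- Probability of early termination: PET = P(X1 ≤ 13).
- Expected sample size: 20 + (1 − PET) × 33.
- P(declare effective) = sum over x = 14 to 20 of P(X1 = x) × P(X2 ≥ 40 − x).

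At p = 0.64, PET = 0.620 (table: 0.62), expected size = 20 + 0.380 × 33 = 32.55 (table: 33), and attained one-sided alpha = 0.0467. At p = 0.80, power = 0.8047 and the chance of stopping at stage 1 is 0.087. The table is reproduced. If every best response of CR or PR is counted, nothing in it changes.

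**2. Margin at the target rate.**

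- Stage 1: expected 20 × 0.80 = 16, needed 14. Three uncounted leave 13, the stopping limit.
- Final: expected 53 × 0.80 = 42.4, needed 40. Three uncounted leave 39.4, below 40.

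Section 6.7 gives different limits (28 patients, continue at 13; 29 of 53 at the end). That conflict with Table S1 is a separate matter. Under those limits the margins are wider: 22.4 expected against 13, and 42.4 against 29.

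**3. Illustration of undercounting.** Let f be the share of true responders not counted, so that the counted rate is 0.80 × (1 − f). The documents give no value for f; the values below are assumptions, applied equally at both stages.

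| Assumed f | Counted rate | Stops at stage 1 | Declared effective (Table S1) |
|---|---|---|---|
| 0 | 0.80 | 0.087 | 0.80 |
| 5% | 0.76 | 0.18 | 0.57 |
| 10% | 0.72 | 0.32 | 0.32 |
| 20% | 0.64 | 0.62 | 0.047 |

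At f = 20% the counted rate equals P0. Under the Section 6.7 limits the chance of declaring the regimen effective is 1.000, 0.997 and 0.93 at f = 0, 10% and 20%.

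**4. When to take the stage 1 count.** Defining best response is not enough if the count is taken the day the 20th patient enrols. The first on-treatment scan comes after cycle 2, at 2 × 28 = 56 days. With even accrual of 30/12 = 2.5 per month, about 2 × 2.5 = 5 of the 20 would have no scan yet. At p = 0.80 the other 15 yield 12 expected responses, and P(at most 13 of 15) = 1 − 15 × 0.8^14 × 0.2 − 0.8^15 = 0.83, against the planned 0.087. The protocol does not say that the count is taken at that moment. It also does not say that it waits.

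**The case against.** The strongest reply is that nobody would run the trial on the literal reading. Section 5.2.1 does not say that response is assessed only after the last dose; it may mean no more than that results are compiled once treatment ends. Section 6.2 points to Section 5 as a whole, which includes the 2-monthly scans and the response definitions. Weekly review of responses and a stage 1 count make little sense unless on-treatment responses count. This stands as evidence of intent: best response is the likely meaning. It does not supply the missing definition, because the one explicit timing sentence points the other way.

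A second reply is that RECIST 1.1 itself may settle the matter. The documents do not reproduce the standard's rule on this, so that cannot be confirmed here. Citing it would in any case leave the protocol's own timing sentence in place.

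A third reply concerns size. The power losses come from an assumed f, and patients still on treatment are, strictly, not yet assessed; no passage says to score them as failures. Both points are right. A reader might infer from the table that the trial is underpowered or that its result will be biased. The documents do not support that: they give no loss figure, and under the likely intent the loss is nil. A reader might also infer that best response makes the result fully comparable with the published 76%. That is not established either, since the protocol does not say how that rate was scored.

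**Conclusion.** The point holds as a conflict in the stated endpoint rule. The only timing given for the primary response, taken literally, does not fit treatment until progression or a stage 1 response count, and the likely intended rule is not written down. The gap is which assessment counts; the categories are clear, because the synopsis and Sections 6.1 and 6.5 supply objective response as CR plus PR.

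Under best response no design figure changes. The firm measure of what is at stake is the margin: about 3 uncounted responders reverse either decision under Table S1 at the target rate. That uses only the protocol's figures and expected counts. The power figures at 5%, 10% and 20% loss show sensitivity only. The point should be corrected before the stage 1 count; it does not call for a new design.

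**What to change.** Delete the timing sentence in Section 5.2.1 and state the endpoint there:

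> The primary efficacy endpoint is the objective response rate: the proportion of patients with a best overall response of CR or PR by RECIST 1.1 at any post-baseline tumour assessment from first dose until progression or start of new anti-cancer therapy.

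Use the same definition in Sections 6.2 and 6.5 and in the stage 1 rule. Leave the status of safety as Section 6.2 gives it.

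Add two rules for the count. Make the stage 1 decision only after every stage 1 patient has had the first scheduled on-treatment scan or has left treatment earlier. Count patients with no post-baseline scan as non-responders.

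Separately, reconcile the passages on the scan after treatment ends: Section 3.1 plans it at 4 weeks, Section 3.2.3 makes it optional, and Section 5.2.3 puts it in the minimum set. The definition above does not depend on how that is settled.

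The cost is a wording amendment and a possible wait of about 2 months at stage 1. The on-treatment scans are already scheduled, Section 3.2.4 already collects the start date of further anti-cancer treatment, and the sample size does not change.

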5.2.2 Secondary Endpoint

Secondary endpoint is overall survival.

5.2.3 Tumor Assessments

Tumor measurements will be performed using RECIST 1.1. At a minimum, CT scans of the head, chest, abdomen, and pelvis will be performed at study entry, every 2 months while on treatment, following the last administration of the test agents, or at any time there is clinical evidence of disease progression, to evaluate disease status.

This section provides the definitions of the criteria used to determine objective tumor response for target lesions using RECIST 1.1.

Complete Response (CR): Disappearance of all target lesions. Any pathological lymph nodes (whether target or non-target) must have reduction in short axis to <10 mm.

Partial Response (PR): At least a 30% decrease in the sum of diameters of target lesions.

Progressive Disease (PD): At least a 20% increase in the sum of diameters of target lesions, taking as reference the smallest sum on study (this includes the baseline sum if that is the smallest on study). In addition to the relative increase of 20%, the sum must also demonstrate an absolute increase of at least 5 mm. (Note: the appearance of one or more unequivocal new metastatic lesions is also considered progression).

Stable Disease (SD): Neither sufficient shrinkage to qualify for PR nor sufficient increase to qualify for PD, taking as reference the smallest sum of diameters while on study.

5.3 Safety Measures

5.3.1 Adverse Events

The investigator is responsible for recording all AEs observed during the study period.

Definition of AE: An AE is any untoward medical occurrence in a patient or clinical investigation subject administered a pharmaceutical product and which does not necessarily have a causal relationship with this treatment.

Definition of Serious Adverse Event (SAE) or serious suspected adverse reaction: A SAE, experience or reaction, is considered serious if, in the view of either the Investigator or Sponsor, it results in any of the following outcomes:

- Results in death;
- Is life-threatening (the patient is at a risk of death at the time of the event; it does not refer to an event that hypothetically might have caused death if it were more severe);
- Requires inpatient hospitalization or prolongation of existing hospitalization: Hospital admissions and/or surgical operations planned before or during a study are not considered AEs if the illness or disease existed before the patient was enrolled in the study, provided that it did not deteriorate in an unexpected way during the study;
- Results in persistent or significant disability/incapacity or substantial disruption of the ability to conduct normal life functions;
- Is a congenital abnormality/birth defect;
- Other: as determined by the Investigator, medically significant events that do not meet any of the criteria above, but may jeopardize the patient and may require medical or surgical intervention to prevent one of the other serious outcomes listed in the definition above.

Clinical laboratory tests will be reviewed for results of potential clinical significance at all timepoints throughout the study. The Investigator will evaluate any change in laboratory values. If the Investigator determines a laboratory abnormality to be clinically significant, it is considered a laboratory AE; however, if the laboratory value abnormality is consistent with a current diagnosis, it may be documented accordingly.

An Adverse Drug Reaction (ADR) is defined as all noxious and unintended responses to a medicinal product related to any dose. An Unexpected Adverse Drug Reaction is defined as any adverse reaction, the nature of which is not consistent with the applicable product information.

Each AE is to be evaluated for duration, severity according to NCI CTCAE v. 4.0, seriousness, and causal relationship to the investigational drug. The action taken and the outcome must also be recorded.

Relationship

The causal relationship between the study drug and the AE has to be characterized as not related, possibly related, or probably related. Events can be classified as “not related” if there is not a reasonable possibility that the study drug caused the AE. A “possible” relationship suggests that the association of the AE with the study drug is unknown; however, the AE is not reasonably supported by other conditions. A “probable” relationship suggests that a reasonable temporal sequence of the AE with the study drug administration exists and, in the Investigator’s clinical judgment, it is likely that a causal relationship exists between the study drug administration and the AE, and other conditions (concurrent illness, progression or expression of disease state, or concomitant medication reactions) do not appear to explain the AE.

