3.2.2.2 Day 15 of First Cycle

On Day 15 of the first 28-day treatment cycle, the following assessments will occur:

- Vital signs (prior to treatment, including: body temperature, respiratory rate, blood pressure, heart rate, weight [kg]);
- Physical examination
- ECOG PS;
- Clinical laboratory assessment (obtained and reviewed prior to treatment: hematology and serum chemistry);
- Collection of AEs.

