5.3.1.1 Reporting of Adverse Events

All AEs, regardless of severity and whether or not they occurred during the study treatment or within 21 days following the last treatment, are to be documented by the Investigator appropriately, including date of onset, severity, action taken, outcome, and relationship to study drug. Adverse events occurring between the time of signing informed consent to the time of the first dose will NOT be captured as AEs unless the AE is a direct result of a study-specific procedure or results in death from an event other than PD.

The Data and Safety Monitoring Plan of the Brown Cancer Center will be used for this phase I/II protocol. The investigators will conduct continuous review of data and patient safety at weekly meetings where the results of each patient’s treatment are discussed. The discussion will include the number of patients, significant toxicities as described in the protocol, dose adjustments, and responses observed. Quarterly summaries of SAEs will be submitted through the CTO to the DSMC for review.

In the case of an SAE, the Investigator must notify the Co-Chairman of the Data Safety Monitoring Committee within 24 hours of becoming aware of the event, and will notify the Institutional Review Board in accordance with its guidelines.

5.3.2 Laboratory Assessments. At Day 1 of each cycle, a CBC with a 3-part differential and a CMP will be ordered and assessed by the Investigator.

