APPENDIX 1: SCHEDULE OF EVENTS

Period	Screening	Day 1 each cycle and End of Treatment	Day 15	Day 1 Cycle 2 then Q2-3 months	Day 1 Cycle 3 (or End of Treatment if PD)	Follow-up for Survival
Assessments	0 to 42 days Pre-treatment	Every 28 days Until PD (± 3 days)	First Cycle Only (± 3 Days)	1 Day (± 7 days) After Cycle 2, and Continue q2-3 Months while on treatment.	1 Day (± 7 days) After final dose in Cycle 2 (and Continue Q2 months Until PD)	Every 3 Months (± 7 days), up to 3 years after last dose
Informed consent	X					
Inclusion/exclusion criteria	X					
Demographic information	X					
TNM staging (AJCC)	X					
Medical history	X					
Vital signs	X	X	X			
Physical exam	X	X	X			
ECOG PS	X	X	X			
Hematology	X	X	X			
Serum chemistry	X	X	X			
2D-Echo	X			X		
Pregnancy test (if applicable)	X					
Dabrafenib/Trametinib & Metformin Initiation		X				
Radiological assessments ^a	X				X	
Adverse events	X	X	X			
Survival information via telephone interview or in-person contact at SOC clinic visit						X

^aCTs of the head, chest, abdomen, pelvis, and other sites of disease will be performed every 2 months, +/- 7 days of Day 1 of the subsequent cycle.

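### As written, sections 5.3.1 and 6.5 report laboratory toxicity through investigator judgment and do not show change from the abnormal values that entry allows (minor)

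*Combined protocol and SAP*

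**What the plan says.** Monitoring the safety of the combination is a primary objective and describing toxicities a secondary one (section 2). The synopsis, under criteria for evaluation, lists "regular monitoring of hematology, blood chemistry, regular measurement of vital signs, and the performance of physical examinations" beside adverse events as ways of assessing safety.

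Laboratory panels are scheduled throughout. Section 5.3.2 says "At Day 1 of each cycle, a CBC with a 3-part differential and a CMP will be ordered and assessed by the Investigator". Section 3.2.2.2 adds Day 15 of cycle 1: "Clinical laboratory assessment (obtained and reviewed prior to treatment: hematology and serum chemistry". Appendix 1 marks hematology and chemistry at screening and in the column "Day 1 each cycle and End of Treatment".

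Section 5.3.1 governs what becomes an adverse event. All timepoints are reviewed and "The Investigator will evaluate any change in laboratory values", but the stated test for recording is "If the Investigator determines a laboratory abnormality to be clinically significant, it is considered a laboratory AE". The same sentence lets an abnormality that fits an existing diagnosis be documented that way. CTCAE comes in afterwards: "Each AE is to be evaluated for duration, severity according to NCI CTCAE v. 4.0, seriousness, and causal relationship to the investigational drug".

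For output, section 6.5 says under its general approach "Descriptive statistics associated with the toxic events will be reported". Under the toxicity objective it promises frequencies and percentages by CTCAE. It mentions no summary of laboratory values.

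**The concern.** Several toxicities that the protocol expects are laboratory findings, often without symptoms. Section 4.5 lists raised AST, low albumin and anemia for trametinib, section 4.3 lists hyperglycemia for dabrafenib, and section 1.2 raises possible low glucose with metformin. If the route into the results is a judgment of clinical significance with no grade that compels recording, two patients with the same value can be reported differently. The reported frequency then depends on recording habits as well as on the drugs.

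The eligibility limits add a second difficulty. Patients may start with abnormal liver, renal or blood values, and a table of event frequencies does not separate a value that worsened on treatment from one that was abnormal at entry. In a single-arm trial no concurrent group is available to calibrate either effect. What is at stake is the completeness and comparability of the laboratory part of the safety description.

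**Working it through.** The plan states no figure on this point, so there is none to reproduce. The check is a comparison of sections, with a little arithmetic for scale.

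**1. From value to table.** Value obtained (5.3.2, 3.2.2.2, Appendix 1) → reviewed by the investigator (5.3.1) → adverse event if judged clinically significant, unless documented under an existing diagnosis (5.3.1) → CTCAE v4.0 grade (5.3.1) → frequency table (6.5). The grade is assigned after the judgment and does not trigger it. The general adverse event definition is broad, but the specific rule for laboratory findings is the judgment.

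**2. Two readings of the CTCAE frequencies in 6.5.**

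| Reading | Asymptomatic abnormality judged not significant | Change from baseline |
|---|---|---|
| Frequencies of recorded adverse events | not in the results | not shown |
| Frequencies that also include directly graded laboratory values | in the results | not shown |

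The first reading fits the wording better, because 5.3.1 attaches CTCAE grading to adverse events and 6.5 speaks of toxic events. The second is not excluded. The missing baseline comparison is common to both.

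**3. Baseline.** Section 3.3.1 admits bilirubin up to 3 × ULN, creatinine up to 2 × ULN, AST or ALT up to 3 × ULN (4 × ULN with liver metastases) and hemoglobin from 8 g/dL. Section 5.3.1.1 does not capture events between consent and first dose, apart from those caused by a study procedure and deaths not due to progression. The adverse event record therefore generally carries no baseline grade. A patient who enters at 3 × ULN bilirubin and stays there and one who rises from normal to 3 × ULN have the same worst value; only a display that crosses baseline with worst value separates them.

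**4. A value-based rate within the protocol.** Section 4.3 cites grade 3 hyperglycemia on dabrafenib at 6% (12/187 = 6.4%) and says that it was based on laboratory values. Section 6.5 does not clearly plan a rate built the same way.

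**5. Size.** Let G be the number of patients with a gradeable abnormality on treatment and R the number in whom it is recorded as an adverse event. The under-count is G − R, and the documents give neither. If the trametinib rates in 4.5 applied to the maximum of 53 patients (an assumption), G would be 0.60 × 53 = 31.8 for AST, 0.42 × 53 = 22.3 for albumin and 0.38 × 53 = 20.1 for anemia. With R unknown, the under-count lies anywhere from 0 to G, which is not an estimate.

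**6. Volume of data.** A patient treated for c cycles has 1 (screening) + c (Day 1 of each cycle) + 1 (Day 15, cycle 1) + 1 (end of treatment) = c + 3 panels. For 53 patients and assumed durations of 3, 6 and 12 cycles, that is 53 × 6 = 318, 53 × 9 = 477 and 53 × 15 = 795 panels. These figures bear on the effort of the fix; they do not count missed toxicity.

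**The case against.** The strongest reply is that recording by clinical significance is a coherent rule. The investigator reviews every result, adverse events are documented whatever their severity (5.3.1.1), they are graded by CTCAE v4.0, and toxicities are discussed weekly. Leaving out trivial deviations is what such a rule is for. The CTCAE wording in 6.5 is loose enough to take in graded laboratory values. On glucose, section 1.2 itself cites a trial in non-diabetic men where fasting glucose fell by only 3% (5.6 to 5.44 mM, and 0.16/5.6 = 2.9%).

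Much of this stands. The rule is not a contradiction, clinical review is real protection for the individual patient, and low glucose may prove uncommon. But review has no planned tabulation, the duty to document every adverse event applies only once something is an adverse event, and even the generous reading of 6.5 leaves change from baseline unshown.

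A reader might go further and infer that the stopping boundary in 6.8 and the phase I grade 4 limit in 6.3 are weakened. The documents do not support that. They do not say whether those counts draw only on judged laboratory events, they give no under-recording rate, and severe abnormalities are the least likely to be dismissed as insignificant.

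**Conclusion.** The point holds as a minor weakness in the safety analysis. Followed as written, and unless 6.5 is meant to include value-graded results, the plan reports asymptomatic laboratory toxicity by case-by-case judgment. It does not show change from the abnormal baselines that entry permits, whichever way 6.5 is read.

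The size of any under-count is unknown. It would be tempting to read the roughly 32, 22 and 20 patients obtained from the trametinib rates as missed toxicity. They are not: section 4.5 gives no grade or method of ascertainment, and many such findings may be recorded, or may be properly judged unimportant. The primary response endpoint is unaffected, and no stated decision rule is shown to be affected. The conclusion rests on the text of 5.3.1 and 6.5 and on no section elsewhere planning a laboratory summary.

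**What to change.** Add the following to section 6.5:

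- Derive CTCAE v4.0 grades by program from the scheduled hematology and chemistry values, for parameters where the value alone defines the grade.
- Report the worst on-treatment grade per patient and parameter, and baseline-to-worst shift tables. Show high and low glucose separately, assuming the chemistry panel includes glucose.
- Keep investigator-judged laboratory adverse events in a separate table, so that both views are visible.

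The recording rule in 5.3.1 can stay, because the value-based tables do not depend on it. If the CTCAE frequencies in 6.5 were always meant to include graded laboratory values, one sentence should say so; the shift tables are still needed.

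The cost is analysis-plan wording and a few tables, with no new visits or tests. There are two downsides. Reported laboratory toxicity may look higher than under judgment-based recording. The protocol also does not say that individual values are captured on the eCRF; if they are not, they must be entered from the clinical record, at c + 3 panels per patient.
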